A sample size of 27 patients will produce a 2-sided exact 80% confidence interval of 34.4% to 62.0% when the sample proportion is 48% (13/27) and an interval of 38.1% to 65.5% when the sample proportion is 52% (14/27). The lower bounds are computed through an exact binomial test.

The Simon's 2-Stage Design will be used in the Phase 2 portion to determine whether CyPep-1 has sufficient anti-tumor activity to warrant further development for patients with advanced or metastatic HNSCC, melanoma, or TNBC. A true ORR ≤9% is considered insufficient to warrant further study (null hypothesis), whereas a true ORR ≥25% is considered sufficiently effective (alternative hypothesis). The number of patients in each stage and the minimum number of patients achieving objective response (CR + PR) per RECIST v1.1 needed to continue to the next stage will be determined based on the Simon's 2-Stage Design with 80% power and a 1-sided significance level of 10% for each arm separately. Based on this design, up to 16 evaluable patients will be accrued for Stage 1. If ≤1 patient of these 16 patients achieves objective response (CR + PR) per RECIST v1.1, the enrollment for the expansion cohort will terminate. Otherwise, 10 additional evaluable patients will be evaluated in Stage 2. In order to enroll the required number of evaluable patients, it is anticipated that approximately 18 and 12 patients (total of approximately 30 patients) will be enrolled into Stages 1 and 2, respectively. Upon completion of Stage 2, if >4 patients out of the total 26 evaluable patients achieve objective response (CR + PR) per RECIST v1.1, then the null hypothesis will be rejected. If the required minimum number of responses is observed prior to completion of enrollment, then the transition between the first and second stages will occur without interruption. If the minimum is not observed at the time enrollment is completed, then enrollment in the second stage will be held until the continuation criterion is met.

SITES: Approximately 35 study sites

SPONSOR:

Cytovation ASA [name]

[contact]

TABLE OF CONTENTS

Sig	gnatur	e Page .		2
Inv	estiga	ator Agi	reement	3
Sy	nopsis	S		4
Ta	ble of	Conten	its	18
Lis	st of T	ables		22
Lis	st of F	igures		23
Lis	st of A	bbrevia	ations and Definition of Terms	24
1	Intro	duction	and Background Information	27
	1.1	Precli	nical and Clinical Data Summary	27
		1.1.1	Preclinical Studies With CyPep-1	27

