- 1. Are 18 years of age or older on the day of signing informed consent;
- 2. Provide written informed consent and are able to comply with study procedures and assessments:
- 3. Have measurable disease per Response Evaluation Criteria in Solid Tumors (RECIST) version (v)1.1 as assessed by the local site Investigator/radiology. Lesions situated in a previously irradiated area are considered measurable if progression has been demonstrated in such lesions;
- 4. Have at least 1 non-ulcerated, measurable, and accessible lesion for intra-tumoral (IT) injection with a maximum diameter of 5 cm;

- 5. Are able to provide tissue from a core or excisional biopsy at screening or have an acceptable stored tumor sample available that was collected within 90 days prior to screening;
- 6. Have an Eastern Cooperative Oncology Group (ECOG) performance status of 0 or 1;
- 7. Have a life expectancy \geq 3 months, as determined by the Investigator;
- 8. Female patients of non-childbearing potential must be either surgically sterile (hysterectomy, bilateral tubal ligation, salpingectomy, and/or bilateral oophorectomy at least 26 weeks before screening), post-menopausal, defined as spontaneous amenorrhea for at least 2 years, or with follicle-stimulating hormone in the post-menopausal range at screening;
- 9. Female patients of childbearing potential (defined as <2 years after last menstruation or not surgically sterile) must have a negative serum pregnancy test at screening and agree to use a highly effective method for contraception from the time of signing the informed consent form (ICF) until at least 120 days after the last administration of study treatment. Highly effective methods of contraception are birth control methods with a failure rate of <1% per year when used consistently and correctly, including the following:
 - Combined estrogen- and progestin-containing hormonal contraception associated with inhibition of ovulation given orally, intravaginally, or transdermally; progestin-only hormonal contraception associated with inhibition of ovulation given orally, by injection, or by implant; intrauterine devices; and intrauterine hormone-releasing systems;
 - Female sterilization (surgical bilateral oophorectomy with/without hysterectomy, total hysterectomy, bilateral tubal occlusion/ligation) at least 26 weeks prior to first study treatment;
 - O Sterilization of male partner (at least 6 months prior to first study treatment dose); and

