 - O Complete sexual abstinence. Periodic abstinence (eg, calendar) and withdrawal are not acceptable. Sexual abstinence is considered a highly effective method only if defined as refraining from heterosexual intercourse during the entire period of risk associated with the study treatment. The reliability of sexual abstinence needs to be evaluated in relation to the duration of the study and the preferred and usual lifestyle of the patient.
- 10. Male patients able to father children must agree to use 2 acceptable methods of contraception throughout the study (eg, condom plus spermicidal gel). Sperm donation is not recommended from the time of signing the ICF until at least 120 days after the last administration of study treatment; and
- 11. Have adequate organ function as defined in Table S2. Specimens must be collected within 72 hours prior to the start of study treatment at Cycle 1 Visit 1.

Table S2. Adequate Organ Function Laboratory Values

System	Laboratory Value
Hematological	
ANC	≥1500/µL
Platelets	≥100,000/µL
Hemoglobin ¹	≥9.0 g/dL or ≥5.6 mmol/L
Renal	
Creatinine OR	≤1.5 × ULN OR
Measured or calculated CrCl ² (GFR can also be used	≥30 mL/min for patients with creatinine levels
in place of creatinine or CrCl)	>1.5 × institutional ULN
Hepatic	
	≤1.5 × ULN OR direct bilirubin ≤ULN for
Total bilirubin	patients with total bilirubin levels >1.5 × ULN
	$\leq 2.5 \times \text{ULN}$ ($\leq 5 \times \text{ULN}$ for patients with liver
AST (SGOT) and ALT (SGPT)	metastases)

This table includes eligibility-defining laboratory value requirements for treatment.

ALT (SGPT) = alanine aminotransferase (serum glutamic pyruvic transaminase); ANC = absolute neutrophil count; AST (SGOT) = aspartate aminotransferase (serum glutamic oxaloacetic transaminase); CrCl = creatinine clearance; GFR = glomerular filtration rate; pRBC = packed red blood cell; ULN = upper limit of normal.

Inclusion Criteria for Arm A

Patients who meet all of the general Inclusion Criteria and the following additional criteria will be eligible for inclusion in Arm A:

- 1. Have histologically confirmed diagnosis of HNSCC (including nasopharyngeal squamous cell carcinoma);
- 2. Have advanced or metastatic HNSCC incurable by standard of care therapies; and
- 3. Have recurrent or metastatic HNSCC that has progressed on or failed both platinum-based chemotherapy AND an immune checkpoint inhibitor (ICI) (given either sequentially or concurrently).

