Radiological assessments and local measurements of tumor lesion(s), according to RECIST v1.1, will be conducted and evaluated at baseline (screening) and at 8-week intervals after the first dose of CyPep-1 through the last Progression Follow-up Visit during the Follow-up Period (up to approximately 26 months after the start of treatment). Radiological assessments can be more frequent if clinically indicated. Magnetic resonance imaging (MRI) or computed tomography (CT) are the preferred scanning procedures to be used in this study. Selection of either MRI or CT should be based on individual patient considerations and local regulations and is at the Investigator's discretion. Once selected for each patient, the same scanning procedure should be used consistently at all remaining visits. Scans will be collected and held centrally for potential central radiologic review. When radiological PD is identified by the Investigator, PD is to be confirmed by another set of scans performed approximately 4 weeks to ≤8 weeks later according to immune-RECIST (iRECIST) guidelines. If PD is not confirmed, study treatment will continue until progression is confirmed.

Patients who have confirmed PD or discontinue treatment for any other reason will be followed-up by phone call every 3 months for survival until the end of study (approximately 26 months after the start of treatment).

Unless death or withdrawal of consent occurs, patients who received any injection of CyPep-1 will have a Safety Follow-up Visit 30 days after the last CyPep-1 injection. If the End of Treatment Visit occurs more than 30 days after the last dose of study treatment, the Safety Follow-up Visit will be skipped. Patients who terminate treatment prior to 18 cycles will continue to be followed for progression every 8 weeks from start of study treatment until the occurrence of confirmed PD as defined by iRECIST or start of new anti-cancer treatment. These patients will also be followed for survival for up to approximately 26 months after the start of treatment.

DOSAGE FORMS AND ROUTE OF ADMINISTRATION:

[figure not shown]
The overall study treatment regimen is defined as IT CyPep-1 in combination with IV pembrolizumab.

CyPep-1 Administration

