Patients who have confirmed PD or discontinue treatment for any other reason will be followed-up by phone call every 3 months for survival until the end of study (approximately 26 months after the start of treatment).

Unless death or withdrawal of consent occurs, patients who received any injection of CyPep-1 will have a Safety Follow-up Visit 30 days after the last CyPep-1 injection. If the End of Treatment (EoT) Visit occurs more than 30 days after the last dose of study treatment, the Safety Follow-up Visit will be skipped. Patients who terminate treatment prior to 18 cycles will continue to be followed for progression every 8 weeks (Q8W) from start of study treatment until the occurrence of confirmed PD as defined by iRECIST (Appendix D) or start of new anti-cancer treatment. These patients will also be followed for survival for up to approximately 26 months after the start of treatment.

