 - o Sterilization of male partner (at least 6 months prior to first study treatment dose); and
 - o Complete sexual abstinence. Periodic abstinence (eg, calendar) and withdrawal are not acceptable. Sexual abstinence is considered a highly effective method only if defined as

refraining from heterosexual intercourse during the entire period of risk associated with the study treatment. The reliability of sexual abstinence needs to be evaluated in relation to the duration of the study and the preferred and usual lifestyle of the patient.

- 10. Male patients able to father children must agree to use 2 acceptable methods of contraception throughout the study (eg, condom plus spermicidal gel). Sperm donation is not recommended from the time of signing the ICF until at least 120 days after the last administration of study treatment; and
- 11. Have adequate organ function as defined in Table 7. Specimens must be collected within 72 hours prior to the start of study treatment at Cycle 1 Visit 1.

Table 7. Adequate Organ Function Laboratory Values

System	Laboratory Value
Hematological	
ANC	≥1500/µL
Platelets	≥100,000/µL
Hemoglobin ¹	≥9.0 g/dL or ≥5.6 mmol/L
Renal	•
Creatinine OR	≤1.5 × ULN OR
Measured or calculated CrCl ² (GFR can also be used	≥30 mL/min for patients with creatinine levels
in place of creatinine or CrCl)	>1.5 × institutional ULN
Hepatic	
	≤1.5 × ULN OR direct bilirubin ≤ULN for
Total bilirubin	patients with total bilirubin levels >1.5 × ULN
	\leq 2.5 × ULN (\leq 5 × ULN for patients with liver
AST (SGOT) and ALT (SGPT)	metastases)

This table includes eligibility-defining laboratory value requirements for treatment.

ALT (SGPT) = alanine aminotransferase (serum glutamic pyruvic transaminase); ANC = absolute neutrophil count; AST (SGOT) = aspartate aminotransferase (serum glutamic oxaloacetic transaminase); CrCl = creatinine clearance; GFR = glomerular filtration rate; pRBC = packed red blood cell; ULN = upper limit of normal.

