8.4 Pregnancy Reporting

If a patient becomes pregnant during the study or within 120 days (30 days if initiates new anti-cancer therapy) after the last dose of study treatment, the Investigator is to stop dosing with study drugs immediately. Early termination procedures should be implemented at that time.

A pregnancy is not considered to be an AE or SAE; however, it must be reported to Medpace Clinical Safety within 24 hours of knowledge of the event. Medpace Clinical Safety will then provide the Investigator/study site the Exposure In Utero (EIU) form for completion. The Investigator/study site must complete the EIU form and fax/email it back to Medpace Clinical Safety.

All exposures during breastfeeding, during the study or within 120 days (30 days if initiates new anti-cancer therapy) after the last dose of study treatment, must be reported by the Investigator to Medpace Clinical Safety as described above.

If the female partner of a male patient becomes pregnant while the patient is receiving study drugs or within 120 days (30 days if initiates new anti-cancer therapy) after the last dose of study treatment, the Investigator should notify Medpace Clinical Safety as described above.

The pregnancy should be followed until the outcome of the pregnancy, whenever possible. Once the outcome of the pregnancy is known, the EIU form should be completed and faxed/emailed to Medpace Clinical Safety. If the outcome of the pregnancy meets the criteria for immediate classification as an SAE (ie, postpartum complication, spontaneous abortion, stillbirth, neonatal death, or congenital anomaly), the Investigator should follow the procedures for reporting an SAE.

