10.3 End of Study

The end of the study ("study completion") is defined as the date of the last protocol-specified visit/assessment for the last patient in the study.

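### Criterion 10 ties male contraception to the study and not to the last dose, so a man who leaves soon after a dose can be released inside the protocol's own 120-day window

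*Protocol*

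**What the plan says.** Criterion 10 appears with the same text in the protocol synopsis and in Section 4.1.1. Its first sentence sets the duty: "Male patients able to father children must agree to use 2 acceptable methods of contraception throughout the study". Its second sentence gives advice with a different end: "Sperm donation is not recommended from the time of signing the ICF until at least 120 days after the last administration of study treatment".

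Criterion 9 requires women of childbearing potential to use highly effective contraception from consent "until at least 120 days after the last administration of study treatment".

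Section 8.4 asks sites to notify a partner's pregnancy that occurs "while the patient is receiving study drugs or within 120 days (30 days if initiates new anti-cancer therapy) after the last dose". That is a reporting rule and does not extend any contraception duty.

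The protocol gives two meanings to the end of the study. Section 3.1.2 places it at about 26 months after the patient's own start of treatment. Section 10.3 says that it "is defined as the date of the last protocol-specified visit/assessment for the last patient in the study".

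Nothing in the supplied protocol or SAP gives men a contraception period counted from the last dose.

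**The concern.** One criterion gives the same man two end-points. The advice on donation follows his last dose. The binding duty on contraception follows the study, which for him may end sooner. An investigator who is asked when contraception may stop finds no answer counted from treatment.

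The gap opens most clearly when a man leaves the study early. Section 4.5.2 lists withdrawal of consent and a sponsor decision to stop among the routes out. The safety visit does not close the gap for a man who withdraws consent, because the rule in Section 3.1.2 begins: "Unless death or withdrawal of consent occurs, patients who received any injection of CyPep-1 will have a Safety Follow-up Visit 30 days after" the last injection. Section 4.5.3 asks staff to make every effort to complete the End of Treatment assessments at 7 (±2) days, but that visit is not guaranteed either.

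At stake is the clarity of a safety-related eligibility criterion. No endpoint, analysis set or error rate depends on it.

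**Working it through.** **Inputs**
- Window that the protocol uses elsewhere: 120 days after the last administration (criteria 9 and 10).
- Treatment: 18 cycles of 6 weeks, with CyPep-1 every 2 weeks (Section 3.1.2). The protocol's 108 weeks reproduces: 18 × 6 = 108.
- Follow-up: about 26 months from the start of treatment (Section 3.1.2).
- Days per month: 30.4375, the divisor in the SAP's survival formulas (Section 3.4.1).
- Assumptions: first dose on day 1, no dose delays, and three CyPep-1 doses per cycle at 0, 14 and 28 days after Visit 1. Because the 26 months is approximate, 25 to 27 months is used as a range.

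**Men who leave the study**

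Uncovered days = 120 − (days from last dose to exit).

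| Exit | Uncovered days |
|---|---|
| On the dosing day | 120 − 0 = 120 |
| At an End of Treatment Visit, day 5 to 9 | 120 − 5 = 115 to 120 − 9 = 111 |
| 30 days after the dose | 120 − 30 = 90 |
| 90 days after the dose | 120 − 90 = 30 |

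The bound is therefore 120 days, and the actual figure depends on the exit date. The last row also applies if a site treats the 90-day serious adverse event period of Section 8.3 as part of the study.

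**Men who stay, if the study means their own participation**
- End of follow-up: 26 × 30.4375 = day 791 (25 months, day 761; 27 months, day 822).
- Latest last dose that still leaves 120 days: 791 − 120 = day 671, or 671 / 7 = 95.9 weeks (range 761 − 120 = 641 to 822 − 120 = 702).
- 18-cycle completer: Cycle 18 Visit 1 is 1 + 17 × 42 = day 715. The last CyPep-1 dose is 715 + 28 = day 743. The 120 days end on 743 + 120 = day 863.
- Gap for that completer: 863 − 791 = 72 days (863 − 822 = 41 to 863 − 761 = 102).
- Men last dosed before about day 671 who stay in follow-up have no gap.
- Section 3.1.2 also allows CyPep-1 alone beyond 18 cycles with no fixed end, so a gap can arise there as well.

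**Men who stay, if the study means the whole trial (Section 10.3)**

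Assume that the last patient is followed to the same month. A man who started d days before that patient is covered to his own day 791 + d. A completer has no gap if 791 + d ≥ 863, that is d ≥ 72 (41 at 27 months, 102 at 25 months). On this reading mainly late-enrolled or withdrawing men are affected.

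**The case against.** The case for leaving the text alone is a fair one. For most men who remain in follow-up, the present wording lasts well beyond 120 days after the last dose. The donation clause is advice and the contraception clause is a duty, so the two need not match. Criterion 9 concerns pregnancy in a treated woman, which is a different exposure. Section 8.4 already puts a 120-day period for partner pregnancies in front of sites. A man who has withdrawn cannot be held to any clause. The SAP (Section 1) reports termination after Phase 1b, which was planned as 6 patients (SAP Section 2.3.5).

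Almost all of this stands, and it limits the size of the point. It does not supply the missing end date. None of these provisions tells a man who leaves early how long the duty lasts, and agreement at entry is what an eligibility criterion governs.

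A reader might go further and infer that partners were exposed to a real hazard, or that men in this trial were released too early. The documents support neither. The supplied text, which lacks the preclinical section, shows no male-mediated reproductive risk. It does not say how many patients were men, when they were last dosed, or whether follow-up continued after termination. The consent form was not supplied and may already state 120 days.

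**Conclusion.** The point holds as a minor internal inconsistency of small reach. Criterion 10 sets an end-point for men that can fall before the 120 days that the protocol uses in the same criterion and in criterion 9. The shortfall is up to 120 days for a man who leaves soon after a dose. On the own-participation reading it is about 72 days (41 to 102) for an 18-cycle completer. These figures rest on an undelayed dosing schedule and on reading about 26 months as day 791, with 25 to 27 months as the range.

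It would be wrong to conclude that men in general are left uncovered. Men last dosed before about day 671 who stay in follow-up are covered on either reading, and most completers are covered if the whole-trial definition applies.

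**What to change.** In the synopsis and in Section 4.1.1, replace the duration in criterion 10 so that the duty runs from the signing of the ICF, throughout the study and "until at least 120 days after the last administration of study treatment", whichever is later. Check that the consent text says the same.

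The additive form matters. Copying the women's end-point alone would shorten the duty for men who stop treatment early and stay in follow-up. With a last dose at Cycle 3 Visit 1 (1 + 2 × 42 = day 85), it would end on 85 + 120 = day 205 instead of about day 791, which is 586 days sooner.

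The cost is one phrase in two places and a check of the consent form, with no added visits, procedures or patients. The downside is a somewhat longer duty for men who leave early or are dosed late. The new wording sets what a man agrees to at entry; it cannot be enforced after he withdraws.

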Figure 2.	One-Stage Study Design	39
Figure 3.	Study Flow	40

[figure not shown]
LIST OF ABBREVIATIONS AND DEFINITION OF TERMS

[figure not shown]
Abbreviation	Definition
AE	Adverse event
AECI	Adverse event of clinical interest
ALT	Alanine aminotransferase
ANC	Absolute neutrophil count
ASCO/CAP	American Society of Clinical Oncology/College of American
	Pathologists
aPTT	Activated partial thromboplastin time
AST	Aspartate aminotransferase
AUC	Area under the curve
CD	Cluster of differentiation
CFR	Code of Federal Regulations
C_{max}	Peak plasma concentration
CNS	Central nervous system
COPD	Chronic Obstructive Pulmonary Disease
COVID-19	Coronavirus Disease 2019
CR	Complete response
CRA	Clinical Research Associate
CSR	Clinical Study Report
CT	Computed tomography
CTA	Clinical trial authorization
CTCAE	Common Terminology Criteria for Adverse Events
DEC	Dose Escalation Committee
DLT	Dose-limiting toxicity
DMC	Data Monitoring Committee
DRF	Dose range finding
EAS	Evaluable Analysis Set
ECG	Electrocardiogram
ECOG	Eastern Cooperative Oncology Group
eCRF	Electronic case report form
EDC	Electronic data capture
EIU	Exposure In Utero
ЕоТ	End of Treatment
FAS	Full Analysis Set
FDA	Food and Drug Administration
GCP	Good Clinical Practice
HIV	Human immunodeficiency virus
HNSCC	Head and neck squamous cell carcinoma

[figure not shown]
Abbreviation	Definition
IB	Investigator's Brochure
ICF	Informed consent form
ICH	International Council for Harmonisation
ICI	Immune checkpoint inhibitor
IEC	Independent Ethics Committee
INR	International normalized ratio
irAE	Immune-related adverse event
IRB	Institutional Review Board
iRECIST	Immune-Response Evaluation Criteria in Solid Tumors
IT	Intra-tumoral(ly)
itRECIST	Intratumoral-Response Evaluation Criteria in Solid Tumors
IV	Intravenous(ly)
LOQ	Limit of quantification
MRI	Magnetic resonance imaging
MTD	Maximum tolerated dose
NCI	National Cancer Institute
ORR	Objective Response Rate
OS	Overall Survival
PD	Progressive disease
PD-1	Programmed cell death protein 1
PD-L1	Programmed cell death ligand 1
PFS	Progression Free Survival
PK	Pharmacokinetic(s)
PR	Partial response
PT	Prothrombin time
Q2W	Every 2 weeks
Q3W	Every 3 weeks
Q6W	Every 6 weeks
Q8W	Every 8 weeks
QTc	Heart rate-corrected QT interval
QTcF	Heart rate-corrected QT interval using Fridericia's formula
RECIST	Response Evaluation Criteria in Solid Tumors
RNA	Ribonucleic acid
RP2D	Recommended Phase 2 dose
SAE	Serious adverse event
SARS-CoV-2	Severe acute respiratory syndrome coronavirus 2
SAS	Safety Analysis Set
SUSAR	Suspected Unexpected Serious Adverse Reaction
t½	Elimination half-life
TEAE	Treatment-emergent adverse event

Abbreviation	Definition	
T_{max}	Time to reach peak plasma concentration	
TNBC	Triple-negative breast cancer	
ULN	Upper limit of normal	
V	Version	

[figure not shown]
[figure not shown]

Figure 1. Individual Time-Serum Profiles for CyPep-1 (CICILIA Study)

computed in only 2 instances, for 1 subject in Cohort 2 and 1 subject in Cohort 3. For 4 additional subjects (3 in Cohort 2 and 1 in Cohort 3) at least 1 sample was quantifiable enabling peak plasma concentration (C_{max}) and time to reach C_{max} (T_{max}) to be computed as sole PK parameters. Descriptive statistics of the computed PK parameters by cohort is provided in Table 3.

Descriptive Statistics of Computed Pharmacokinetic Parameters by Cohort Table 3.

To date in the CICILIA study, the most frequently reported treatment-emergent adverse event (TEAE) was "injection site pain" and occurred in all 3 dose cohorts. No fatal TEAE or SAE/Suspected Unexpected Serious Adverse Reactions (SUSARs) were reported. Additionally, no TEAE leading to CyPep-1 discontinuation was reported; see Table 4 which shows data from the Safety Report of the CICILIA study part I (dose escalation).

The most common CyPep-1-related adverse event (AE) was "injection site pain" and was reported in Cohorts 2 and 3.

Table 4. Cumulative Treatment-Emergent Adverse Events and CyPep-1-Related Treatment-Emergent Adverse Events by Preferred Term (CICILIA Study)

		Grade 1	Grade 2 (n	Grade 3/4	All Grades		
Cohort	AE PT	(n events)	events)	(n events)	(n events)	SAE/SUSARS	
Cumulative	e TEAEs per PT						
1	Constipation	3	0	0	3	0	
1	Injection site pain	2	0	0	2	0	
2	Anaemia	0	1	1	2	0	
2	Cough	1	1	0	2	0	
2	Fatigue	1	1	0	2	0	
2	Injection site pain	5	1	0	6	0	
2 2	Nausea	2	0	0	2	0	
2	Cancer pain	1	2	0	3	0	
2	Urinary tract						
	infection	0	2	0	2	0	
2	Vomiting	1	0	1	2	0	
3	Cancer pain	7	6	1	14	0	
3	Constipation	3	1	0	4	0	
3	Fatigue	2	0	0	2	0	
3	Injection site pain	15	1	0	16	0	
Cumulative	e CyPep-1-related TEA	Es per PT					
3	Injection site pain	11	1	0	12	0	
2	Injection site pain	5	1	0	6	0	
2	Fatigue	0	1	0	1	0	
1	Pyrexia	1	0	0	1	0	
2	Nausea	1	0	0	1	0	
2	Rash macular	1	0	0	1	0	
2	Vomiting	1	0	0	1	0	
3	Injection site						
	oedema	1	0	0	1	0	
3	Pain in extremity	1	0	0	1	0	
3	Platelet count						
	decreased	1	0	0	1	0	
3	Skin wound	1	0	0	1	0	
3	Vitiligo	1	0	0	1	0	

AE = adverse event; n = number of subjects; PT = preferred term; SAE = serious adverse event; SUSAR = Suspected Unexpected Serious Adverse Reaction; TEAE = treatment-emergent adverse event.

[figure not shown]
Source: Investigator's Brochure for CyPep-1

Analysis of the reported TEAEs across the dose cohorts showed no increase in the number of TEAEs per subject in the higher dose levels; see Table 5.

Table 5. Frequency of Reported Treatment-Emergent Adverse Events per Dose Cohort (CICILIA Study)

	Cohort 1 (n=3)			Cohort 2 (n=5)			Cohort 3 (n=6)		
Relatedness	Mild	Moderate	Severe	Mild	Moderate	Severe	Mild	Moderate	Severe
Not related									
TEAE	10	2	7	12	9	5	20	9	3
Related TEAE	1	0	0	8	2	0	16	1	0
n = number of subjects; TEAE = treatment-emergent adverse event.									
Source: Investigator's Brochure for CyPep-1									

Additionally, CyPep-1 is currently being evaluated in a randomized, placebo-controlled, double-blind, single center Phase 1 study as topical formulation administered to subjects with cutaneous warts (Study CHDR1803).

[figure not shown]

[figure not shown]
This Phase 1b/2a study will assess the efficacy, safety, and pharmacodynamics of CyPep-1 when administered directly into measurable tumor lesions in combination with the anti-PD-1 antibody pembrolizumab. Additionally, the study will assess anti-tumor effects of CyPep-1 on injected lesions and non-injected target lesions identified at baseline, as well as local and systemic immunological effects of CyPep-1 in combination with pembrolizumab.

